7.1.2. Important Potential Risks

(1) Interstitial lung disease

Rationale: In Study B1931022 and Study B1931006 involving subjects other than patients with relapsed or refractory ALL, interstitial lung disease occurred in the inotuzumab ozogamicin group. Interstitial lung disease may affect the benefit-risk balance of inotuzumab ozogamicin. Thus, if it is reported in the special investigation, applicable patients will be extracted and evaluated.

(2) Inflammatory gastrointestinal events

Rationale: In Studies B1931022 and B1931010, and Studies B1931003, B1931004 and B1931008 involving subjects other than patients with relapsed or refractory ALL, inflammatory gastrointestinal events occurred in the inotuzumab ozogamicin group. Gastrointestinal mucosal inflammation and ulcers may affect the benefit-risk balance of inotuzumab ozogamicin. Thus, if they are reported in the special investigation, applicable patients will be extracted and assessed.

(3) QTc interval prolonged

Rationale: In Study B1931022, QTc interval prolonged related to inotuzumab ozogamicin occurred in the inotuzumab ozogamicin group. Thus, if it is reported in the special investigation, applicable patients will be extracted and examined.

(4) Reproductive toxicity

Rationale: While no exposure during pregnancy or lactation was reported in clinical studies, findings in the reproductive organs, and embryos and fetuses were obtained in nonclinical studies. Thus, if it is reported in the special investigation, applicable patients will be extracted and evaluated.

7.2. Research Objectives

The following matters will be investigated in patients receiving BESPONSA under actual conditions of use after marketing:

(1) Occurrence of adverse events (AEs) (including the following evaluations):

Background characteristics possibly affecting the onset of liver disorder including VOD/SOS, myelosuppression, infections and hemorrhage, and grade ≥ 3 events based on the CTCAE v4.0 as well as risk factors for early death of HSCT patients after BESPONSA treatment

(2) Efficacy (hematologic remission rate and survival)

8. RESEARCH METHODS

8.1. Study Design

This is a multicenter, cohort study in patients receiving BESPONSA. The investigators will complete case report forms (CRFs) based on the information required for the study that will be extracted from medical records created in daily medical practice.

8.2. Setting

All patients receiving BESPONSA will be included in this investigation.

PFIZER CONFIDENTIAL

CT24-WI-JPN-GPSP01-RF09 8.0 Non-Interventional Study Protocol Template for Secondary Data Collection

Study 01-Nov-2023

Page 13 of 33

Inotuzumab

B1931024 NON-INTERVENTIONAL STUDY PROTOCOL

Amended 8, 12 December 2023

[INDICATION]

Relapsed or refractory CD22-positive ALL

[DOSAGE AND ADMINISTRATION]

The usual dosage for adults is 0.8 mg/m² (body surface area) of inotuzumab ozogamicin (genetical recombination) on Day 1 and 0.5 mg/m² (body surface area) on Days 8 and 15 once daily by intravenous infusion over at least 1 hour followed by a treatment-free interval. The length of cycle is 21 to 28 days for Cycle 1 and 28 days for Cycles 2 and subsequent cycles. The treatment should be repeated. The number of cycles should be decided while taking account of the schedule of HSCT. The dose should be decreased as necessary according to the patient's condition.

8.3. Study Sites

The investigation will be conducted at approximately 200 sites mainly the departments of hematology and internal medicine.

8.4. Planned Study Period

The planned period of this investigation is as follows:

Study period: For 5 years from the start date of releasing BESPONSA to the market*

Registration period: From the start date of releasing BESPONSA to the market to 30 April 2020*

*: Patients starting to receive BESPONSA on or before 30 April 2020 will be registered in this investigation regardless of the registration period and CRFs will be collected.

8.5. Study Method

A central registration all-patient surveillance system will be used for this investigation. Patients applicable to the investigation will be registered until meeting the target sample size. Registration to the investigation will be made by entering information in the electronic data capture (EDC) system for post-marketing drug investigation on the Internet which will be provided by the sponsor within approximately 2 weeks after the start of BESPONSA treatment (or after concluding a contract).

The sponsor will check that patients who have started treatment with BESPONSA by 30 April 2020 have been registered using the EDC system or paper form.

After it is confirmed that the target information can be collected, patient registration and request for new CRF completion will be ended. However, the system for taking prompt measures should be maintained in preparation for the cases in which additional investigation, etc. is judged to be necessary from the viewpoint of safety measures, etc., and is instructed by the Pharmaceuticals and Medical Devices Agency or the Ministry of Health, Labour and Welfare (MHLW).

8.6. Contract

A written agreement on the implementation of this investigation should be, in principle, concluded with the head of the site before delivering BESPONSA, and then BESPONSA should be delivered. However, even if BESPONSA is given to a patient before concluding the agreement due to therapeutic priority, the patient should be registered in the investigation. If specified agreement documents are available at the sites, they should be respected.

PFIZER CONFIDENTIAL

CT24-WI-JPN-GPSP01-RF09 8.0 Non-Interventional Study Protocol Template for Secondary Data Collection

Study 01-Nov-2023

Page 14 of 33

Inotuzumab

B1931024 NON-INTERVENTIONAL STUDY PROTOCOL

Amended 8, 12 December 2023

8.7. Observation Period

Observation period: The observation period will be 52 weeks for patients not undergoing HSCT within 52 weeks after the start of BESPONSA treatment or until 52 weeks following HSCT for patients undergoing it within 52 weeks after the start of BESPONSA treatment. For a patient starting BESPONSA treatment before 30 April 2020 who is transferred to another hospital during the observation period, the conclusion of the agreement on the implementation of this investigation should be requested to the hospital to which the patient has been transferred, and data from there should be collected to the extent possible.

(1) Treatment phase

From treatment initiation to Day 28 post-treatment: Safety (e.g., AEs) and efficacy (hematologic remission and survival)

(2) Follow-up phase

From Day 29 post-treatment to Week 52 (patients who did not undergo HSCT before Week 52) or 52 weeks after HSCT (patients who underwent HSCT before Week 52): Safety (VOD/SOS) and efficacy (survival)

8.8. Variables

The following information obtained during the observation period in the investigation is defined as survey items.

Table 1. Schedule of Observation

Variables	Registration form	Booklet 1		Booklet 2
		Baseline	Treatment phase*	
Patient background	ID number	●	○	
	Gender	●	○	
	Birth month and year (age at the start of the investigation if it is not provided)	●	○	
	Experience of participation in this investigation	●	○	
	(Planned) start date of BESONSA treatment	●		
	Target disease of the investigation	●		
	Informed consent from the patient (BESONSA treatment)* ³	●		
	Informed consent from the patient (publication of the investigation results)* ⁴	●	○	
	Patient registration number at the site from which the patient is transferred	●	○	
	Name of the site from which the patient is transferred	●	○	
	Height and weight		●	
	Target disease		●	
	Date of confirming the initial onset		●	
	Chromosomal karyotype		●	
	Medical history		●	
Treatment and clinical status	Treatment history at baseline (remission induction chemotherapies and HSCT from the initial onset)		●	
	BESONSA treatment record		↔↔	
	Pregnancy status		↔↔	
	Clinical laboratory tests (hematology, hepatic function test, renal function test, electrocardiography, pancreatic function test, bone marrow test)		●	▲
	ECOG PS	●	▲	▲
	Treatment of the target disease after the start of BESONSA treatment (HSCT, HSCT donor information, drug therapy, non-drug therapy)		↔↔	↔↔
	Prophylactic treatment for reducing infusion reactions		↔↔	
	Prophylactic treatment for preventing and reducing tumour lysis syndrome		↔↔	
	Clinical evaluation (hematologic remission and MRD)		↔↔	

PFIZER CONFIDENTIAL

CT24-WI-JPN-GPSP01-RF09 8.0 Non-Interventional Study Protocol Template for Secondary Data Collection

Study 01-Nov-2023

Page 16 of 33

Adverse events	Any AEs			↔	
	VOD/SOS			↔	↔
Records of treatment end/discontinuation			●		
Records of investigation continuation/discontinuation			●		●
Confirmation of survival (including reasons for death)			↔		↔

*: From treatment initiation to Day 28 post-treatment

*2: From Day 29 post-treatment to Week 52 (patients who did not undergo HSCT before Week 52) or 52 weeks after HSCT (patients who underwent HSCT before Week 52)

*3: Informed consent for BESPONSA treatment should be obtained after adequately explaining the efficacy of and risks from BESPONSA to the patient.

*4: Informed consent should be obtained whenever possible for disclosing the results from this investigation at academic conferences, in papers and/or through other relevant means.

●: Data entry or items to be entered; O, If there is no change in data, data in the registration form should be used as those in the CRF.

▲: HSCT pretreatment data should be entered for patients who underwent HSCT after the initiation of BESPONSA treatment only.

8.8.1. Patient Characteristics

The following information at the start of BESPONSA treatment will be entered or recorded:

- (1) ID number
- (2) Gender
- (3) Birth month and year (age at the start of the investigation if it is not provided)
- (4) Height and weight
- (5) Target disease (name of disease, WHO Classification 4th edition, relapsed or refractory)
- (6) Date of confirming the initial onset
- (7) Chromosomal karyotype
- (8) Medical history (VOD/SOS, graft versus host disease [GVHD], hepatitis, liver disease, other diseases)
- (9) Experience of participation in this investigation
- (10) Patient registration number at the site from which the patient is transferred (for transferred patients)
- (11) Name of the site from which the patient is transferred (for transferred patients)
- (12) Informed consent from the patient (BESPONSA treatment)*
- (13) Informed consent from the patient (publication of the investigation results)

Informed consent should be obtained whenever possible for disclosing the results from this investigation at academic conferences, in papers and/or through other relevant means.

- (14) Target disease of the investigation*
- (15) (Planned) start date of BESPONSA treatment*

*: Items to be entered in the registration form only

The following items will not be collected from transferred patients:

Informed consent from the patient (BESPONSA treatment)

Informed consent from the patient (publication of the investigation results)

Height and weight

Inotuzumab

B1931024 NON-INTERVENTIONAL STUDY PROTOCOL

Amended 8, 12 December 2023

Target disease (name of disease, WHO Classification 4th edition, relapsed or refractory)

Date of confirming the initial onset

Chromosomal karyotype

ECOG PS (baseline)

Medical history (VOD/SOS, GVHD, hepatitis, liver disease, other diseases)

Target disease of the investigation

(Planned) start date of BESPONSA treatment

8.8.2. History of Treatment for the Target Disease at Baseline

- (1) Remission induction chemotherapy (remission induction chemotherapeutics, number of treatments, and response)
- (2) HSCT (type of transplantation, date of transplantation, and type of pretreatment drugs)

These items will not be collected from transferred patients.

8.8.3. Targeted Drug Use Record (Actual Treatment Record)

- (1) Date of dosing
- (2) Single dose
- (3) Number of cycles administered

8.8.4. Records of BESPONSA Treatment End/Discontinuation

- (1) Whether or not the treatment is completed or discontinued
- (2) Date of completion or discontinuation
- (3) Reason for completion or discontinuation
(disease progression or worsening of general condition, AEs, not making another visit, remission, transfer to another hospital or department, or other)

8.8.5. Treatment for the Target Disease after the Start of BESPONSA Treatment

- (1) HSCT (type of transplantation, date of transplantation, and type of pretreatment drugs)
- (2) HSCT donor information (alternative donor or matched related donor)
- (3) Drug therapy (name of drug, start date, and route of administration)
- (4) Non-drug therapy (radiotherapy, plasma transfusion included: name of therapy and start date)

8.8.6. Prophylactic Treatment for Reducing Infusion Reactions (Presence or Absence)

8.8.7. Prophylactic Treatment for Preventing and Reducing Tumor Lysis Syndrome (Presence or Absence)

8.8.8. Clinical Laboratory Tests

- (1) Hematology (red blood cell count, hemoglobin, hematocrit, white blood cell count, differential white blood count, peripheral blast cells and platelet count)
- (2) Hepatic function test (AST [GOT]*, ALT [GPT]*, AL-P, γ-GTP, total bilirubin*)

*: Data on the upper limit of normal (ULN) at the site will be entered.

- (3) Renal function test (BUN, creatinine)
- (4) Electrocardiography (QT, QTc)

PFIZER CONFIDENTIAL

CT24-WI-JPN-GPSP01-RF09 8.0 Non-Interventional Study Protocol Template for Secondary Data Collection
Study 01-Nov-2023

Inotuzumab

B1931024 NON-INTERVENTIONAL STUDY PROTOCOL

Amended 8, 12 December 2023

(5) Pancreatic function test (amylase, lipase)

(6) Bone marrow test (myeloblast)

8.8.9. Records of investigation discontinuation

For patients who withdraw from the investigation during the observation period, enter the date of discontinuation. For the main reason for discontinuation, i.e., why the investigation cannot be continued, select one of the following options.

(Not making another visit, death, transfer to another hospital or department, or other)

8.8.10. ECOG PS (Eastern Cooperative Oncology Performance Status)

(1) Date of assessment

(2) Assessment results

8.8.11. Clinical Evaluation

8.8.11.1. Hematologic Remission

Response will be assessed according to the following response criteria, and the best overall response during the observation period will be entered. However, if subsequent treatment for the target disease is started or HSCT is performed, the best overall response before the start of the subsequent treatment or HSCT, whichever is earlier, will be entered.

Response criteria

1. CR
 - No peripheral blasts or extramedullary disease (no lymphadenopathy, splenomegaly, or skin/gum infiltration/testicular mass/CNS involvement)
 - Trilineage hematopoiesis (TLH) and <5% blasts
 - Absolute neutrophil count (ANC) >1,000/ μ L
 - Platelets >100,000/ μ L
 - No recurrence for 4 weeks
2. CRi (CR with incomplete count recovery)
 - Recovery of platelets but <100,000/ μ L or ANC is <1,000/ μ L
3. Progressive disease (PD)
 - Increase of at least 25% in the absolute number of peripheral blood or bone marrow blasts or development of extramedullary disease
4. Relapsed disease
 - Reappearance of blasts in the blood or bone marrow (>5%) or in any extramedullary site after CR
5. Inevaluable

Inotuzumab

B1931024 NON-INTERVENTIONAL STUDY PROTOCOL

Amended 8, 12 December 2023

8.8.11.2. Minimal Residual Disease (MRD)

If a MRD test gives a negative result during the observation period, the earliest date will be entered. However, if subsequent treatment for the target disease is started or HSCT is performed, MRD will be assessed before the start of the subsequent treatment or HSCT, whichever is earlier.

8.8.12. Confirmation of Survival

The following information will be entered to assess the overall survival during a period from the start date of BESPONSA treatment to the end date of the observation period:

Result of confirmation of survival at the end of the observation period, date of confirming the survival status if the patient is alive, date of death if the patient died (when the date of death is unknown, the last date of confirming survival), reason for death

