## 6. ENDPOINTS AND COVARIATES

### 6.1. Safety Endpoints

- Adverse events: All undesirable or unintended signs or symptoms that occurred after administration of this drug, regardless of causal relationship
- Adverse drug reactions: Adverse events assessed as causally related to this drug by the physician

- Serious adverse events or serious adverse drug reactions: Adverse events or adverse drug reactions assessed as serious by the physician

- Death after HSCT:

- Time to death after HSCT: Days and weeks from the date of first HSCT after the start of this drug to the date of death
- Event: Death (for any cause)
- Censoring: The patient is confirmed alive at the time of completion or discontinuation of the survey. The endpoint will be censored on the day when patient's survival was last confirmed.

Early death after HSCT is defined as the above event that occurred within 100 days after the first HSCT after the start of this drug. Early death is supposed to be absent if the patient died on 101 days or later, or was confirmed alive at the time of completion/discontinuation of the survey.

- Transplant-related death after HSCT (non-relapse death):

- Time to transplant-related death after HSCT: Days and weeks from the date of first HSCT after the start of this drug to the date of death.
- Event: Death due to non-tumor-related causes, resulting from worsening of the target disease of this drug
- Competing risks: Death due to tumor-related causes, resulting from worsening of the target disease of this drug
- Censoring: The patient is confirmed alive at the time of completion or discontinuation of the survey. The endpoint will be censored on the day when patient's survival was last confirmed.

Early transplant-related death after HSCT (non-relapse death) is defined as the above event that occurred within 100 days after the first HSCT after the start of this drug. Early death is supposed to be absent if the patient died on 101 days or later, or was confirmed alive at the time of completion/discontinuation of the survey.

- Transplant-unrelated death after HSCT (relapse death):

- Time to transplant-unrelated death after HSCT: Days and weeks from the date of first HSCT after the start of this drug to the date of death.
- Event: Death due to tumor-related causes, resulting from worsening of the target disease of this drug
- Competing risks: Death due to non-tumor-related causes, resulting from worsening of the target disease of this drug

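### Deaths after HSCT are labelled non-relapse or relapse from the recorded reason for death alone; relapse after HSCT is not listed as collected, so some post-relapse deaths may be counted as transplant-related

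*Protocol*

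**What the plan says.** **Endpoint definition (SAP 6.1).** The transplant-related, non-relapse endpoint is defined as "Event: Death due to non-tumor-related causes, resulting from worsening of the target disease of this drug", with "Competing risks: Death due to tumor-related causes, resulting from worsening of the target disease of this drug". The relapse endpoint is the mirror image. Neither definition refers to whether the patient had relapsed before dying, and relapse itself is not a competing event. The early version of each endpoint is "the above event that occurred within 100 days after the first HSCT after the start of this drug".

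**Use (SAP 8.2.3.3).** The split feeds three outputs: a tabulation of deaths up to and beyond 100 days, cumulative incidence curves estimated out to Week 104, and a factor analysis of early transplant-related death that repeats the one for all early deaths.

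**Data on cause (Protocol 8.8.12).** The survival item collects "date of death if the patient died (when the date of death is unknown, the last date of confirming survival), reason for death". The protocol gives no attribution rule and no adjudication.

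**Data on relapse (Protocol 8.8.11.1).** For patients who go to transplant or further treatment, "the best overall response before the start of the subsequent treatment or HSCT, whichever is earlier, will be entered". The relapsed-disease category therefore cannot record a relapse after HSCT.

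**Nearest indirect marker (Protocol 8.8.5).** Later treatment of the target disease is recorded, including "Drug therapy (name of drug, start date, and route of administration"). Non-drug therapy is recorded by name and start date.

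**The concern.** In transplant work, non-relapse mortality means death without prior relapse. Here the label is attached to something else: death for which a non-tumor reason was recorded. The two differ for patients who relapse after HSCT and then die of infection, hemorrhage or another complication.

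If such deaths are recorded under the complication, the cumulative incidence of transplant-related death is too high and that of relapse death too low. The factor analysis of early transplant-related death includes blast counts, salvage line, best response and MRD. These plausibly also predict relapse, so misplaced deaths could make them look like predictors of transplant toxicity. What is at stake is how the cause-specific results are read, in a survey that includes risk factors for early death after HSCT among its objectives.

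**Working it through.** **Step 1. Can any collected variable identify relapse after HSCT?**

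| Variable | Collected until | Shows post-HSCT relapse? |
|---|---|---|
| Best hematologic response (Protocol 8.8.11.1) | HSCT or next treatment, whichever is earlier | No |
| MRD (Protocol 8.8.11.2) | HSCT or next treatment, whichever is earlier | No |
| Laboratory values including blasts (Protocol 8.8, Table 1 and notes) | Baseline, then HSCT pretreatment values | No |
| AEs other than VOD/SOS (Protocol 8.8.14) | Day 28 post-treatment | Not systematically |
| VOD/SOS, survival, reason for death (Protocol 8.7, 8.8.12) | 52 weeks after HSCT | Only through the stated reason for death |
| Later drug and non-drug therapy (Protocol 8.8.5, Table 1) | Through follow-up | Indirectly; no indication is listed |

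The SAP does not use the last row in its death definitions. Its listed drug-therapy summary (SAP 8.2.2) stops at the end of the treatment period, and SAP 7 uses the start dates to define the last observation date.

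**Step 2. Size.** The plan gives no figure for this endpoint, so there is none to reproduce. Every input below is an assumption.

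*Simple product.* Overcount at Day 100 = P(relapse by Day 100) × P(death by Day 100 given relapse) × P(non-tumor reason recorded).
- All inputs low: 0.15 × 0.30 × 0.20 = 0.009, or 0.9 points.
- All inputs high: 0.30 × 0.50 × 0.40 = 0.060, or 6.0 points.

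*Illness-death model with constant hazards* (HSCT to relapse to death). Let p be the Day-100 incidence of true non-relapse death, assumed equal to that of relapse, with p = 10%, 15% or 20%. Then a = −ln(1 − 2p)/100 per day, and each of the two hazards is a/2. Let d = ln 2 / (median survival after relapse), with a median of 60 or 120 days. Deaths after relapse by time t are

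X(t) = (a/2) × [(1 − e^(−at))/a − (e^(−dt) − e^(−at))/(a − d)].

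If a share s of these deaths (10% to 50%) carries a non-tumor reason, the overcount is s × X(t).

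- Smallest case (p = 10%, median 120 days, s = 10%): X(100) = 2.5%, overcount 0.2 points. X(364) = 17.7%, overcount 1.8 points.
- Largest case (p = 20%, median 60 days, s = 50%): a = −ln(0.6)/100 = 0.00511, d = 0.01155, X(100) = 8.7%, overcount 4.4 points. X(364) = 36.6%, overcount 18.3 points.

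| p | True non-relapse death, Day 100 | By reason for death, Day 100 | True, Week 52 | By reason for death, Week 52 |
|---|---|---|---|---|
| 10% | 10.0% | 10.2–12.1% | 27.8% | 29.6–39.1% |
| 15% | 15.0% | 15.4–18.2% | 36.4% | 38.8–51.6% |
| 20% | 20.0% | 20.5–24.4% | 42.2% | 45.1–60.5% |

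**Step 3. Against sampling error.** The documents do not give the number of recipients. Assume 30% to 50% of 176, or 53 to 88. Then 0.9 points is 0.5 to 0.8 of a patient, and 6.0 points is 3.2 to 5.3 patients. With 9 events in 60 recipients (15%), the exact 95% interval is 7.1% to 26.6%. At Day 100 the overcount is small beside that interval. Unlike sampling error, it leans one way.

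**The case against.** The strongest reply is that misclassification is possible but not shown. The case report form is not among the documents, so the options for reason for death cannot be seen. SAP 6.1 ties the tumor side to worsening of the target disease, and an investigator could record a fatal infection during uncontrolled relapse there. A reader might infer that every infection or hemorrhage death after relapse is counted as transplant-related. The documents do not support that: such deaths may be so counted, and no stated rule settles it.

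A second reply is that SAP 6.1 contradicts itself by describing non-tumor deaths as arising from worsening of the target disease, and that correcting this clause might move some deaths to the tumor side. That is fair, and it depends on the correction chosen. No correction of wording supplies a relapse date, so the label would still exceed the data.

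A third reply is that the stated objective is barely touched. A reader might infer that the early-death objective is compromised. It is not: SAP 6.1 defines early death as death from any cause within 100 days, and its factor analysis does not use the split. The cause-specific factor analysis is an addition, SAP 4.1 treats all testing as exploratory, and Protocol 8.14 already warns of incomplete chart data. All of this stands and limits the weight of the point.

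Nor is it shown that blast counts, MRD or salvage line would emerge as false predictors of toxicity. That is a risk to interpretation, and it has not been quantified.

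**Conclusion.** The point holds as one of labelling and interpretation. A rule based on recorded cause alone, with no post-HSCT relapse data listed, cannot deliver non-relapse and relapse mortality. The likely error is upward for non-relapse death and downward for relapse death.

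Its size cannot be taken from the documents. Under assumed rates it runs from near zero to about 6 points at Day 100 (0.9 to 6.0 by the simple product, 0.2 to 4.4 by the model) and about 2 to 18 points at Week 52 by the model. The 6.0 needs all three assumptions at their upper limits. These ranges are illustrations and should not be read as estimates of the bias in this survey.

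Affected: the tabulation and cumulative incidence by cause, and the factor analysis of early transplant-related death. Unaffected: all-cause early death after HSCT and overall survival. The change is worth making because it is nearly free and alters what may be concluded about transplant toxicity.

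**What to change.** 1. In SAP 6.1, in SAP 8.2.3.3 and in the factor analysis, rename the two endpoints *death from non-tumor cause* and *death from tumor cause*. State that relapse after HSCT was not collected, so these are not non-relapse and relapse mortality.

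2. Add a sensitivity analysis to the cumulative incidence and to the early-death factor analysis by cause. Deaths after the first antileukemic drug or radiotherapy for the target disease started after the first HSCT (Protocol 8.8.5 start dates) go to the relapse side. Exclude plasma transfusion, which 8.8.5 includes under non-drug therapy, along with other supportive therapy and drugs given as conditioning.

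3. State the limits of the proxy. It misses relapse that was never treated, and it reads maintenance or pre-emptive therapy as relapse, because no indication is listed. It gauges how far the cause-based result could shift and does not replace it.

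Cost: SAP wording and one extra analysis on dates already collected. No new data field is requested; Protocol 5 planned the end of data collection for May 2024, before SAP version 6.0 of September 2024.
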